1.1 Investigational Agents

This study includes 2 investigational agents, *Tapentadol* and *Tramadolhydrochlorid*, and 1 inert placebo.

Tapentadol is a centrally acting analgesic acting as a μ -opioid receptor agonist and as a norepinephrine reuptake inhibitor (5). The analgesic effect of Tapentadol is direct without conversion to a pharmacologically active metabolite.

Tramadolhydrochlorid is a centrally acting analgesic acting as a μ -opioid receptor agonist, induction of serotonin release, and inhibition of norepinephrine reuptake (6;7). The analgesic effect of Tramadolhydrochlorid is almost exclusively mediated through the pharmacologically active metabolite O-desmethyltramadol, a potent μ -opioid receptor agonist.

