1.5 Population

When investigating the potential differences in dizziness and gait ataxia between different opioid types in a population that has pain it is difficult to discern the effects of pain relief from central nervous system side effects, because pain relief in itself may affect gait variability in a way that may mask gait ataxia. Therefore, a healthy control group without pain is included because dizziness and gait ataxia in this population with confidence can be attributed to side effects on motor function in the central nervous system (gait ataxia). This information can be used to distinguish between increased gait variability caused by pain relief from centrally derived gait ataxia in the patient population.

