3.1 Study Design/Type

The study is designed as an experimental single center, double-blind treatment, cross-over study with inert *placebo*, *Tapentadol* (Palexia Depot), and *Tramadolhydrochlorid* (Mandolgin Retard), with a minimum of 7days wash-out periods.

At day 1 (Visit 1), baseline measurements are carried out before tablet administration. Immediately after baseline measurements one tablet is administered, and hourly measurements are performed for 6 hours. Subsequently all participants enter a minimum 7 day washout period, after which they return to the facility to repeat the procedures at Visit 2 (day 8+) and Visit 3 (day 15+). The order of treatments will be randomized (1:1:1). The design is illustrated below:

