3.2 Primary Study Endpoints/Secondary Endpoints

Primary outcome:

- Change from the post-washout baseline in gait variability over time Secondary outcomes:
 - Change from the post-washout baseline in autonomous nerve system assessments over time
 - Change from the post-washout baseline in plasma concentrations of opioid metabolites over time
 - Change from the post-washout baseline in participant assessment of dizziness, nausea, and other adverse effects over time
 - Change from the post-washout baseline in knee pain (patients only) using 100 mm
 Visual Analogue Scale (VAS) over time

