5 OUTCOME ASSESSMENTS

5.1 Gait ataxia (primary outcome):

Gait ataxia is assessed using biomechanical gait analyses. 3-D kinematic gait data is obtained using reflective markers, arranged in the Plug-in-Gait configuration and a 6-camera Motion Analysis System sampling at 100 Hz. Ground reaction forces and moments are obtained with two 6-channel force platforms operating at 1500 Hz. The participants walk a distance of 10m 25 times at self selected comfortable speed, while kinematic and kinetic data is recorded. 25 series of gait cycles will be recorded.

From the gait analyses gait ataxia is quantified as step-to-step variability. Ataxia is defined as increased (or excess) variability during normal walking.

CONFIDENTIAL

12

The analyses of gait ataxia are done at The Parker Institute, Copenhagen University Hospital at Frederiksberg.

5.2 Autonomous nerve system (secondary outcome):

The autonomic nervous control of heart rate and blood pressure will be analyzed through the use of quantitative test of maximal capacity as well as of ambient activity. Blood pressure and interbeat intervals will be recorded continuously on a beat by beat basis by CNAP-monitor (photoplethysmography) and by one standard precordial lead in the ECG. The maximal capacity will be quantified from the Valsalva manoeuvre primarily using the blood pressure response during phase 2 as a measure of sympathetic activity. Further quantification will be made by deep breathing test analyzing heart rate changes as a measure of parasympathetic function. The ambient activity will be measured from spontaneous fluctuations in heart rate through the use of both time and frequency analysis as well as by deterministic methods.

The analyses of autonomous nerve system are done at Syncope Center, Copenhagen University Hospital at Frederiksberg.

5.3 Plasma concentrations of opioid metabolites (secondary outcomes):

Blood samples are drawn from the cubital region every hour for 7 hours (7 samples) during each study visit. 10 ml is drawn at each time point (70 ml each visit, total 210 ml throughout the study). For storage of the samples a research bio-bank is established. The purpose of the bio-bank is to store the biological material safely and controlled until batch analyses can be performed. Once analyses have been completed, the material will be destroyed. The material is stored for a maximum 5 years and is subsequently destroyed – irrespective of whether analyses have been completed or not.

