The analyses of plasma concentrations of active ingredients and metabolites are done at The Faculty of Pharma, University of Copenhagen.

5.4 Patient reported dizziness (secondary outcome; appendix F):

Current self reported dizziness is measured every hour for 7 hours (7 samples) during each study visit. Dizziness is measured using a Visual Analog Scale (VAS) ranging from 0–100 (0=no dizziness; 100=worst imaginable dizziness) with 101 point resolution on a validated electronic touch screen.

5.5 Knee pain (secondary outcome; appendix G):

Current knee pain is measured every hour for 7 hours (7 samples) during each study visit. The VAS for measuring pain intensity is an acceptable measure used in many chronic pain trials. This study will use a VAS ranging from 0-100 (0=no pain; 100=worst imaginable pain) with 101 point resolution on a validated electronic touch screen.

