7 STATISTICAL PLAN

7.1 Statistical Methods

All data analyses will be carried out according to this prespecified analysis plan. Analyses are done applying SAS software (v. 9.2; SAS Institute Inc., Cary, NC, USA). The repeated measures of changes from the wash-out baseline assessment (hour 0 at each visit) are analyzed using a Repeated-Measures Analysis of Covariance (via PROC MIXED): a factor for

drug (Tapentadol, Tramadolhydrochlorid, and Placebo), a factor for time (hour; 6 levels), group (healthy controls and patients) drug-by-time, drug-by-group, group-by-time, and drug-by-time-by-group interactions, with the daily baseline values as covariates. Participants will be handled as a random factor.

In case of non-normal distribution, data transformation may be necessary.

Estimated least-squares mean effects over each individual Time point (Hours 1-6) will be reported for each drug and group. All estimated means will be presented with standard errors and 95% confidence intervals. For the differences between drugs, significance tests (p-values) will be shown.

Exploratory analyses are done with demographic variables and the secondary outcomes (plasma concentration of opioid metabolites, autonomous nerve system, pain and self-reported dizziness) as covariates, to assess the effects of these on the primary outcome.

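### Section 7.1 reads post-dose outcomes, entered as covariates, as effects on gait, and its plasma covariate is defined by metabolites although tapentadol acts as the parent drug

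*Protocol*

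**What the plan says.** Protocol section 7.1 first sets out the main model: change in gait variability from the hour-0 value of each visit, with drug, time, group and their interactions, the daily baseline as covariate and participant as random factor. Between-drug p-values are announced for that model. It then adds: "Exploratory analyses are done with demographic variables and the secondary outcomes (plasma concentration of opioid metabolites, autonomous nerve system, pain and self-reported dizziness" are used "as covariates, to assess the effects of these on the primary outcome".

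The other relevant statements are:

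- Timing (section 3.1): "Immediately after baseline measurements one tablet is administered, and hourly measurements are performed for 6 hours". Section 5 adds for plasma "Blood samples are drawn from the cubital region every hour for 7 hours (7 samples) during each study visit" and for dizziness "Current self reported dizziness is measured every hour for 7 hours (7 samples) during each study visit". Knee pain follows the same hourly schedule (section 5.5).
- Active compounds (section 1.1): "The analgesic effect of Tapentadol is direct without conversion to a pharmacologically active metabolite". For tramadol, the same section attributes analgesia almost wholly to O-desmethyltramadol.
- Assays: section 5.3 carries metabolites in its heading, but its closing sentence says that active ingredients and metabolites are both analysed.
- Pain (section 3.2): "Change from the post-washout baseline in knee pain (patients only". Section 5.5 does not repeat the restriction.

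**The concern.** A covariate slope can be read as an effect only if the covariate is not itself a result of treatment and shares no unmeasured causes with the outcome. A drug given minutes to hours before can change dizziness, pain, autonomic tone and gait together. A dizziness slope may then show only that both respond to the same central action, and a reader told that it is an effect would conclude that dizziness disturbs gait.

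The plasma term has a second problem. Followed to the letter, it gives tapentadol visits an exposure variable that section 1.1 says does not carry the drug's activity. The pain term has a third: it exists for one of the two groups only, while the model in the same section is built around a group factor.

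At stake is the interpretation of the exploratory results. The answer to the trial's main question does not depend on these models.

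**Working it through.** The plan attaches no figure to this sentence, so there is nothing to reproduce. The check sets the sections side by side, counts records, and writes the covariate argument in symbols, because the documents give no values to put in.

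**1. Are the covariates post-dose?** Seven hourly samples (section 5) equal hour 0 plus the six hours after the tablet (section 3.1). Plasma, dizziness and pain at hours 1 to 6 are therefore all post-dose. Section 5.2 gives no clock times for the autonomic tests, but section 3.2 defines that outcome as change from baseline over time, which is also post-dose.

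**2. What does the slope estimate?** The text does not say whether drug stays in the exploratory model.

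- Drug left out: the slope combines the within-drug association with the difference between drug and placebo visits, so it is confounded by drug.
- Drug kept: let D be drug and U a visit-level central response, U = D + V, where V varies between visits. Let dizziness = aU + noise and gait = gU + noise, with no effect of dizziness on gait. Write ρ for the share of the within-drug variance of dizziness that comes from V. The fitted dizziness slope is (g/a)ρ where the true effect is 0, and the fitted drug coefficient is g(1 − ρ) where the total drug effect is g.
- Drug kept, different structure: let pain = −aD + S + noise and gait = bD + cS + noise, where S is a day-level cause that does not depend on drug. With r the share of the within-drug variance of pain that comes from S, the pain slope is cr (true value 0) and the drug coefficient is b + acr.

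For positive coefficients, the first structure shrinks the drug coefficient and the second inflates it. Both vanish only when the shared share (ρ or r) or the coefficients on the common cause are zero. The failure of the effect reading is general. Its size and direction are not, and nothing in the documents fixes ρ, r, a or c.

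**3. Plasma.** Two readings of the plasma covariate are possible.

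- Literal (metabolites): for tapentadol this is not the active compound under section 1.1.
- Loose (whichever compound was assayed, in one column): with drug in the model, the common slope is (β₁v₁ + β₂v₂)/(v₁ + v₂), where β is each drug's own slope and v its concentration variance in raw units. The compound with the larger concentration variance dominates. Placebo visits should carry no study drug and add nothing to the within-drug slope.

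**4. Pain.** Post-dose records for 24 completers (section 7.2): 24 × 3 visits × 6 hours = 432. With pain in the model and recorded in patients only: 12 × 3 × 6 = 216. PROC MIXED omits records with a missing covariate, so the 216 that remain are all from patients. Group is then constant, and group, drug-by-group, group-by-time and the three-way term cannot be estimated.

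**The case against.** The strongest reply is that the analyses are labelled exploratory, that relating gait to exposure or symptoms is legitimate, and that the form of such models is usually left to an SAP, which is not at hand. Much of this stands. The protocol does not state that drug stays in these models, that covariates enter jointly, or that one plasma slope is fitted. It does not say that a drug effect will be read from them, and the main model already contains no post-dose covariate. What the reply does not remove is stated text: section 7.1 calls itself the prespecified plan, gives the purpose as assessing effects, and names metabolites as the exposure.

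Three stronger readings are tempting and are not supported.

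- A reader might infer that the plan throws away half its sample. The restriction to 12 patients applies only to a model containing pain, and it is the same after the fix, because a patients-only outcome has no other data. Models with plasma, autonomic measures or dizziness keep all 24 unless pain is entered with them, which the protocol does not say.
- A reader might infer that the trial's separation of pain relief from central ataxia rests on the pain covariate. Section 1.5 assigns that task to the pain-free controls, of whom it says "This information can be used to distinguish between increased gait variability caused by pain relief from centrally derived gait ataxia in the patient population". The main model carries that contrast in its drug-by-group terms.
- A reader might want a number for the bias. Any such number would come from chosen inputs, and as shown above even its direction depends on them.

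**Conclusion.** The point holds, at low severity. Three things in the exploratory sentence need correcting: post-dose outcomes are read as effects, the exposure is named by metabolites although tapentadol's activity lies in the parent drug, and a patients-only covariate is placed beside a model with group terms. The between-drug comparison on the primary outcome is unaffected, and the demographic covariates in the same sentence are not open to the objection.

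The only size that can be stated is the record count for a pain model: 216 of 432, from 12 participants.

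The conclusion rests on these assumptions:

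- The active analyte for gait is taken to be the one section 1.1 names for analgesia.
- Section 5.3 gives no assay list, so it is assumed that its reference to active ingredients and metabolites covers tapentadol itself and O-desmethyltramadol.
- Section 3.2, and not the silence of section 5.5, is taken to decide who records pain. If controls record it too, the loss of records and of group terms does not arise.

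**What to change.** Replace the exploratory sentence in section 7.1 with wording to this effect:

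- Drug effects on gait variability are read only from the main model, without post-dose covariates.
- Gait is related to plasma concentration separately within each active drug, using that drug's own active analyte: tapentadol on tapentadol visits and O-desmethyltramadol on tramadol visits.
- Gait is related to knee pain in patients only, without group terms and separately from the other covariates. Sections 3.2 and 5.5 should agree on who records pain.
- Autonomic measures and dizziness are analysed apart from pain. Results for all post-dose variables are reported as exploratory associations and not as effects.

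Given the assays described in section 5.3, no new data should be needed. The cost is a few extra model statements and a more modest interpretation. The change should be made before unblinding.

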7.2 Sample size considerations

No previous studies exist on the effects of opioids on gait ataxia, so it is not possible to make sample size estimations based on previous data from similar studies. However, one study investigating changes in gait variability using the same methodology have shown significant increases in gait variability during dual task walking (walking and talking) on a sample of elderly (age above 70 years) with intact cognition. Gait variability increased by 0.05 (arbitrary unit) during dual task walking (P=0.03). Extrapolating these results to the present study, a sample size of 24 will make it possible to detect a mean difference of 0.03 arbitrary units (at the P=0.05 level) with a power of 80.4%

Because it is assumed that the gait ataxia induced by opioids will be significantly more pronounced than what is induced by dual task walking (walking while talking), and due to practical considerations a total of 24 participants (12 healthy volunteers and 12 patients) that complete the protocol (defining the per-protocol population) will be included in the analyses.

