7.4 Significance

Tests of statistical significant difference between the two investigational products for all endpoint analyses will use a significance level of 0.05.

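### The 80.4% power figure does not follow from the dual-task results it is said to extrapolate: no SD is given, and the SD it needs equals the quoted mean increase

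*Protocol*

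**What the plan says.** Protocol section 7.2 states that no earlier study of opioids and gait ataxia exists. It borrows from one study of dual-task walking in elderly people: "Gait variability increased by 0.05 (arbitrary unit) during dual task walking (P=0.03"). By extrapolation, it credits 24 participants with the ability to "detect a mean difference of 0.03 arbitrary units (at the P=0.05 level) with a power of 80.4"%. It states no SD, no within-participant correlation, no test, no sidedness and no size for the borrowed study.

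The same section gives two further grounds for 24 completers (12 healthy volunteers and 12 patients). One is an expectation that opioid-induced ataxia will exceed the dual-task effect. The other is practicality.

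On the analysis, section 7.1 plans a mixed model with drug, time and group and all their interactions, and says "Estimated least-squares mean effects over each individual Time point (Hours 1-6) will be reported for each drug and group". Section 7.4 says that tests between the two investigational products "will use a significance level of 0.05".

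**The concern.** Power for a mean difference needs a difference, a sample size, a significance level and a measure of spread. Section 7.2 supplies the first three. The borrowed result (a mean and a P value) yields a spread only if the reference sample size and the test are also known, and neither is given. The decisive input is therefore missing from a figure quoted to three digits.

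The SD that returns 80.4% in the natural test for a cross-over is 0.050, and the only 0.05 on the outcome scale in section 7.2 is the mean increase. If that mean was taken for the SD, the figure says nothing about the variability of the outcome.

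This is the only power figure in the protocol. A reader of a non-significant tapentadol-tramadol comparison would go to it to judge whether a difference of 0.03 could have been missed.

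**Working it through.** **Inputs from protocol section 7.2:** difference 0.03; n = 24 completers; significance level 0.05; stated power 80.4%; reference mean increase 0.05 with P = 0.03.

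**Assumptions supplied here, because the protocol does not state them:** a two-sided test; a paired t-test on within-participant differences, since every participant receives all three products; and, for the reference study, a paired test of dual-task against single-task walking.

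**Step 1. Reproduce the stated figure.**
- Power = P(|T| > t(0.975, n−1)), where T is noncentral t with n−1 degrees of freedom and noncentrality √n × difference/SD.
- With SD = 0.05, the standardised difference is 0.03/0.05 = 0.60, the noncentrality is 0.60 × √24 = 2.94, and the critical value on 23 degrees of freedom is 2.069.
- Power = 80.37%, which rounds to 80.4%.
- Solving backwards, a rounded 80.4% requires an SD between 0.04995 and 0.05001.

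**Step 2. Try other tests.** An SD other than 0.05 is needed to reach 80.4% with:
- one-sided paired test: 0.0570
- normal approximation: 0.0522
- unpaired comparison, 12 against 12: 0.0249
- unpaired comparison, 24 against 24: 0.0361

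None of these values appears in the protocol.

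**Step 3. Is an SD of 0.05 compatible with the quoted P value?** If mean and SD of differences were both 0.05, then t = 0.05/(0.05/√N) = √N. The two-sided P is 0.038 at N = 7, 0.0255 at N = 8 and 0.0115 at N = 10. An SD of 0.05 therefore fits the quoted result only for a reference sample of about 7 or 8, or 9 if rounding of the 0.05 and the 0.03 is allowed for.

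**Step 4. Back-calculate the SD and recompute power.** SD = 0.05 × √N / t(0.985, N−1). For N = 12, this is 0.05 × 3.464/2.491 = 0.0695.

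| Reference N (not stated) | Implied SD of differences | Power for 0.03, n = 24 |
|---|---|---|
| 5 | 0.034 | 98.6% |
| 6 | 0.041 | 93.2% |
| 7 | 0.047 | 85.3% |
| 8 | 0.052 | 77.1% |
| 10 | 0.061 | 63.0% |
| 12 | 0.070 | 52.6% |
| 20 | 0.095 | 31.5% |
| 30 | 0.120 | 21.7% |

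Rounding of the quoted values moves these figures but not the pattern. At N = 10, the most favourable case (mean 0.045, P = 0.025) gives an SD of 0.053 and power of about 76%.

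**Step 5. Express the sample size without an SD.** The standardised difference detectable with 80% power is 0.597 SD for 24 completers and 0.889 SD for 12.

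**The case against.** The arithmetic is not wrong: 80.4% reproduces to the digit once an SD of 0.05 is supplied. Section 7.2 never says where its SD came from. It could be a genuine SD of differences, or a per-visit SD of 0.05 with a correlation of 0.5, since 0.05 × √(2 × 0.5) = 0.05. The match is also to a number quoted to one significant figure. All of this stands, so a reader who infers that the mean was entered as the SD goes further than the document allows.

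A reader might also infer that the trial lacks the power it claims. That is not shown either. With a reference sample of 7 or fewer, the back-calculated power at the quoted values is 85% or more.

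Nor is the figure the only ground for 24. Section 7.2 also relies on practicality and on an expected effect above 0.05. For a difference of 0.05, power with 24 is 92.1% at the SD implied by N = 12 and 80.3% at N = 16, falling to 49.8% at N = 30. But that expectation is given without data. It also concerns ataxia induced by opioids, not the size of a difference between two of them.

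Finally, the by-group and by-hour reporting might seem to undercut the figure. With SD 0.05, a group of 12 has 47.5% power for 0.03. Section 7.2, however, makes its claim for all 24 and for no subgroup, so this limits the reach of the figure without refuting it. A similar argument, that a contrast of two changes from baseline has a larger SD than one same-session difference, has no settled direction: the baseline covariate and the six hourly measurements can reduce variance.

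What remains is that the power statement is presented as following from results that do not yield it.

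**Conclusion.** The point holds as a should-fix. The 80.4% in section 7.2 cannot be obtained from the mean and P value it is said to extrapolate. In a two-sided paired test it rests on an unstated SD of 0.050, which coincides with the quoted mean increase. Taken at face value, the quoted results support 80% or more only if the reference sample was about 7 or fewer (up to about 9 with the most favourable rounding). From 10 upward, power for 0.03 is 63% or less at the quoted values, and about 76% or less with the most favourable rounding.

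A shortfall is likely but not established, because the reference sample size is unknown and the paired test is an assumption. The documents do not establish how the SD was chosen. The sample size is not called into question.

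**What to change.** In section 7.2, replace 80.4% with a power figure based on a stated SD of the within-participant drug difference. Give its source (the reference study's own SD, or one back-calculated from its P value and sample size), the test and its sidedness.

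If no SD is available, say so and state that 24 completers give 80% power, two-sided at 0.05, for a pooled pairwise drug difference of about 0.60 SD. Add a short table of power for 0.03 with 24 participants:

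| SD of differences | Power |
|---|---|
| 0.03 | 99.7% |
| 0.04 | 94.0% |
| 0.05 | 80.4% |
| 0.06 | 65.0% |
| 0.08 | 42.1% |
| 0.10 | 29.1% |
| 0.12 | 21.7% |

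In either case, add that the figure covers one pooled drug contrast, and that a contrast within one group of 12 has 80% power for about 0.89 SD.

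The cost is one rewritten paragraph. The stated power will probably look less favourable. Sample size, design and analysis are unchanged.
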